Objectives	
1.1 PRIMARY OBJECTIVES Sub-Study 1 (home quarantined COVID-19 patients): Median time to release from quarantine by meeting the following criteria: 1) No fever for 72 hours without the use of fever-reducing medications 2) improvement in other symptoms and 3) 7 or 10 days have elapsed since the beginning of symptom onset, as determined by CDC guidelines at the time. The first date of quarantine will be considered the date of SARS-CoV-2 nasopharyngeal swab test that confirmed positivity.
 
Sub-Study 3 Healthcare worker prophylaxis: Rate of COVID-19 infection at 2 months
 
1.2 SECONDARY OBJECTIVES Sub-Study 1: Rate of participant-reported secondary infection of housemates, rate of hospitalization, rate of treatment related adverse events Sub-Study 3: rate of treatment related adverse events
 
1.3 CORRELATIVE OBJECTIVE To bank serially collected samples to enable correlative science related this trial

Number of Subjects	Sub-Study 1: 100; interim analysis after 34 and 68 Sub-Study 3: 200; interim analysis after 50 and 100 Total: 300
Diagnosis and Main Inclusion/Exclusion Criteria	
 • Age ≥ 18 years old (Sub-study 3) • Competent and capable to provide informed consent

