13.0 STATISTICAL CONSIDERATIONS

13.1 Sample size calculation

Because we are uncertain about the outcome values for both control and treatment arms of the study, we will use group-sequential methods, initially proposing a real difference that is small, and allowing us to stop early for both efficacy and futility. We conduct two interim analyses and a final analysis, after approximately 1/3, 2/3, and 100% of subjects have completed. We will use the Hwang-Shih-DeCani alpha spending rules. Boundaries for efficacy and futility decisions are show below. Futility boundaries are non-binding.

z-value	Boundaries		Information Proportion
	Stage Efficacy	Futility	
1	2.7819	-0.8235	0.3400

The PATCH Trial			
	p-value	Boundaries	Information
Stage	Efficacy	Futility	Proportion
2	2.2653	0.4262	0.6800
3	1.6813	1.6813	1.0000
1	0.00270	0.79490	0.3400
2	0.01175	0.33497	0.6800
3	0.04636	0.04636	1.0000

Because we are uncertain about the outcome values for both control and treatment arms of the study, we will use group-sequential methods, initially proposing a real difference that is small, and allowing us to stop early for both efficacy and futility. We conduct two interim analyses and a final analysis, after approximately 1/3, 2/3, and 100% of subjects have completed. We will use the Hwang-Shih-DeCani alpha spending rules. Boundaries for efficacy and futility decisions are show below. Futility boundaries are non-binding.

Sub-Study 1, Home quarantined patients with COVID-19: The first date of quarantine will be considered the date of SARS-CoV-2 nasopharyngeal swab test that confirmed positivity.

The CDC guidelines for release from quarantine change during the course of this study. The original criteria were: 1) 72 hours without a fever 2) improvement in symptoms 3) 7 days since the beginning of symptoms have elapsed. The new criteria are: 1) 72 hours without a fever 2) improvement in symptoms 3) 10 days since the beginning of symptoms have elapsed. Our original sample size calculation was as follows:

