Sub-Study 3, prophylaxis in hospital workers: The transmission of SARS-COV2 from patient to hospital worker depends on many factors including specifics of standard care to prevent transmission, but especially on the number of patients seen at a given hospital or outpatient practice. Across China the reported hospital worker infection rate is 3.8%, but in Wuhan it is reported as 58% at the height of the epidemic. We will use a

10% transmission rate as the null hypothesis (low dose group). In order for HCQ to be considered effective our alternative hypothesis will be a 1% transmission rate. With a 1:1 randomization for the HCQ to control arms we would require a total of 200 hospital worker subjects total for Arm 4. With the placebo group of 100 subjects and the h HCQ arm of 100 subjects, a one-sided z-test ($\alpha=0.05$) comparing the rates in the two groups would have an 80% power to detect a significant difference when the difference in the population rates

The *PATCH Trial* is at least 9%.

The *hypothesis* will be tested using a one-sided test, with a z-score corresponds to the log of the odds-ratio for recovery between the two groups. We will obtain the estimate of the odds ratio, and 95% CI, from logistic regression.

Interim analysis: We will perform two interim analyses at 25% and 50% completion of participant enrollment, testing for early efficacy or futility, using z-score boundaries that follow Hwang-Shih-DeCani alpha spending rules. Following those rules, we have 84% power using 100% of the sample, if our under our 10% versus 1% scenario is true. Under those circumstances, we have a 6% chance of stopping for early efficacy at the first interim analysis. We also have an 81% chance of stopping early for efficacy at the first interim analysis if the low dose arm really has 45% infection instead of 10%. Under normal circumstances (10% v 1%), we have a 27% chance of stopping for early efficacy at the second interim analysis. We also have an 80% chance of stopping early for efficacy at the second interim analysis if the low dose arm really has 23% infection instead of 10%.

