1. Substudy 1 Interim analysis 1: after 34 out of a target 100 evaluable patients have completed the study and the report is available for review
2. Substudy 1 Interim analysis 2: after 68 out of a target 100 evaluable patients have completed the study and the report is available for review

Substudy 3

1. Substudy 3 Interim analysis 1: after 50 out of a target 200 evaluable patients have completed the study and the report is available for review
2. Substudy 3 Interim analysis 2: after 100 out of a target 200 evaluable patients have completed the study and the report is available for review

This DSMB is coordinated by the Sponsor. DSMB meetings are held by teleconference. All three members of the DSMB must be present to hold a DSMB meeting. Critical decisions of the DSMB are made by unanimous vote whenever possible, or majority vote if this is not possible.

While the Medical Monitor will review deviations, unanticipated serious adverse events and safety data, she may consult the DSMB as needed.

Meeting Format

DSMB meetings are organized into open and closed sessions. Data reviewed by the DSMB is provided by the Sponsor.

Open Sessions

Data presented in the open session may include enrollment data, individual adverse event data, baseline characteristics, overall data accuracy and compliance data or issues, and other administrative data. The DSMB also considers data from other studies or external sources as made available during its deliberations.

During the open sessions, prepared summary reports and tables are reviewed and discussed by the DSMB.

Facilitator(s) (e.g., member of Sponsor and/or investigator team responsible for the report preparation) and observers from University research oversight committees may attend the DSMB meeting Open Sessions as necessary in order to facilitate data presentation, follow-up reporting, and answer questions posed by the DSMB.

Closed Sessions

The closed session is restricted to the DSMB members. Data which may compromise the integrity of the study (e.g., comparative data) is analyzed and discussed only in the closed session. Details of closed session deliberations (e.g., minutes) are considered privileged and not subject to disclosure except as required by law.

Meetings conclude with a recommendation to continue, modify, pause, or terminate the study. In addition, recommendations for modification, pause, or termination may be endorsed for perceived safety concerns based on clinical judgment.

DSMB Reports

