The primary analysis will consist of a z-test, corresponding to the log of the odds-ratio for the proportion well in the HCQ group, versus the proportion well in the placebo group at the end of 8 weeks. The estimate will be made using either logistic regression or directly using contingency table methods. Tests will be one-sided, with type one error based on the alpha spending plan, with an overall type one error of 5%.

Interim Analysis

We will perform two interim analyses at 25% and 50% completion, testing for early efficacy or futility, using z-score boundaries that follow Hwang-Shih-DeCani alpha and beta spending rules (Z-value boundaries are shown in the table below).^{1,2} Following those rules, we have 84% power using 100% of the sample, if our infection rate in placebo compared to hydroxychloroquine is 10% versus 1% scenario is true. Under those circumstances, we have a 6% chance of stopping for early efficacy at the first interim analysis. Under normal circumstances (10% vs 1%), we have a 27% chance of stopping for early efficacy at the second interim analysis. We also have an 80% chance of stopping early for efficacy at the second interim analysis if the low dose arm really has 23% infection instead of 10%. Results of the interim analysis will be presented to the Data Safety and Monitoring Board (DSMB) by the study team. The DSMB will provide a recommendation of continuing or terminating the study early.

Z-Value Boundaries			
	Boundaries		Information
Stage	Efficacy	Futility	Proportion
1	2.9473	-1.2318	0.2500
2	2.5825	-0.2676	0.5000
3	1.6664	1.6664	1.0000

P-Value Boundaries			
	Boundaries		Information
Stage	Efficacy	Futility	Proportion
1	0.00160	0.89099	0.2500
2	0.00491	0.60550	0.5000
3	0.04782	0.04782	1.0000

References

- 1- Hwang, I. K., Shih, W. J., and De Cani, J. S. (1990). Group sequential designs using a family of Type I error probability spending functions. *Statistics in Medicine* 9, 1439– 45.
- 2- Jennison, C. and Turnbull, B. W. (2000). *Group Sequential Methods with Applications to Clinical Trials*. Chapman and Hall/CRC, Boca Raton, FL.

Final analyses

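### Protocol 13.1 triggers the Sub-Study 3 interim looks by enrolment, but the printed boundaries and the charter assume 50 and 100 participants with completed 8-week follow-up

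*Protocol*

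**What the plan says.** The Sub-Study 3 interim paragraph of Protocol 13.1 reads: "We will perform two interim analyses at 25% and 50% completion of participant enrollment, testing for early efficacy or futility". Other current text gives a different basis, or none:

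- Protocol 13.1, opening rule for all sub-studies: looks come "after approximately 1/3, 2/3, and 100% of subjects have completed". The fractions are not those of Sub-Study 3, but the unit is the completed subject.
- DSMB charter, Subsequent Meetings: "Substudy 3 Interim analysis 1: after 50 out of a target 200 evaluable patients have completed the study" and "Substudy 3 Interim analysis 2: after 100 out of a target 200 evaluable patients have completed the study". The SAP repeats both triggers under DSMB Meetings.
- SAP, Interim Analysis: "We will perform two interim analyses at 25% and 50% completion, testing for early efficacy or futility". It does not say completion of what.
- Protocol Study Summary: "Sub-Study 3: 200; interim analysis after 50 and 100". No basis is given.

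Protocol and SAP print one Sub-Study 3 boundary table, fixed at information 0.25, 0.50 and 1.00. The primary outcome is infection status at 8 weeks (SAP, Primary Analysis), and missing values are not imputed (SAP, Missing Data). For Sub-Study 1, Protocol 13.1 also speaks of enrolment, but it then ties each look to 10 days of follow-up and sets the boundaries from the information available at the time. Sub-Study 3 has neither qualifier.

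**The concern.** With an 8-week outcome, the 50th enrolment and the 50th completed participant are different moments. A team following 13.1 literally would bring data to the DSMB earlier than the charter provides and compare them with boundaries built for more information. The interim decisions are what is at stake: the chance of an efficacy stop, the chance of a wrong futility stop, and the second-look step in which conditional power between 0.5 and 0.8 can lead to a larger sample size. Nothing in the Sub-Study 3 text corrects for a look that arrives with the wrong amount of information.

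**Working it through.** **1. Reproduce the plan's figures.** Inputs from Protocol 13.1: one-sided alpha 0.05, Hwang-Shih-DeCani spending, 10% versus 1%, 100 per arm. The spending parameter is not stated; a value of −4 reproduces the table.

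- Cumulative alpha at information t is 0.05(1 − e^(4t))/(1 − e^4): 0.00160 at 0.25, 0.00596 at 0.50, 0.05 at 1. With non-binding futility the bounds come out at 2.9473, 2.5825 and 1.6664, as printed.
- The chance of crossing bound z with n per arm is Φ[(0.09 − z·s0)/s1], with s0 = √(2 × 0.055 × 0.945/n) and s1 = √((0.09 + 0.0099)/n).
- n = 25: (0.09 − 2.9473 × 0.0645)/0.0632 = −1.58, giving 5.7% (stated 6%).
- n = 50: (0.09 − 2.5825 × 0.0456)/0.0447 = −0.62, giving 26.7% (stated 27%).
- The alternative scenario of 45% infection at look 1 gives 81.0% (stated 81%), and 23% at look 2 gives 80.3% (stated 80%).

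The plan's figures therefore assume 50 and 100 evaluable participants with a known outcome.

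**2. Information under an enrolment trigger.** Assumption: 200 participants enrol uniformly over A weeks. The documents give no Sub-Study 3 accrual rate. The trial lasts about one year, so 52 − 8 = 44 weeks is the longest accrual that fits. Completers when k are enrolled = max(0, k − 8 × 200/A); information = completers/200.

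| A (weeks) | Completers at 50 / 100 enrolled | Information |
|---|---|---|
| 16 or less | 0 / 0 | 0 / 0 |
| 26 | 0 / 38 | 0 / 0.19 |
| 32 | 0 / 50 | 0 / 0.25 |
| 40 | 10 / 60 | 0.05 / 0.30 |
| 44 | 13.6 / 63.6 | 0.07 / 0.32 |

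The 4-week swab and earlier clinical tests also carry some information. Crediting those still in follow-up with half a participant each, the 44-week case adds 0.5 × 36.4 = 18.2 to each look: 31.8/200 = 0.16 and 81.8/200 = 0.41.

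**3. Effect on the looks.** Using the formula of step 1 at 44 weeks and completers only (6.8 and 31.8 per arm), the plan's 6% and 27% become 1.2% and 15%. Expected infections under the design rates (n × 0.11) fall from 2.75 to 0.75 at look 1 and from 5.5 to 3.5 at look 2.

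**4. Operating characteristics with the printed bounds.** Simulated Brownian paths (4,000,000 per case), drift 2.66, which gives the stated 84% power:

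| Information | Efficacy stop, look 1 | False futility stops, both looks | Power, futility followed | Power, futility ignored | Type I error, futility ignored |
|---|---|---|---|---|---|
| 0.25 / 0.50 | 5.3% | 1.9% | 83.8% | 84.2% | 0.0500 |
| 0.16 / 0.41 | 3.0% | 3.1% | 83.1% | 84.2% | 0.0507 |
| 0.07 / 0.32 | 1.2% | 6.0% | 81.1% | 84.2% | 0.0514 |

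At 40 weeks (0.05/0.30) the false futility stops are 7.0%, power with futility followed is 80.3%, and type I error with futility ignored is 0.0518. If futility is followed, type I error stays below 0.05 in every row.

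**The case against.** The strongest reply is that the enrolment phrase is loose wording. Everywhere else that a unit is named, it is the completed participant, and Protocol 11.5 refers to the charter for the DSMB's operational details. Sub-Study 1 uses a similar phrase and then explains it in terms of follow-up. The DSMB is advisory, the futility bounds are non-binding, and the size of any shortfall rests on an accrual rate that the documents do not state. Slow early accrual would narrow the gap, and partial follow-up recovers part of it.

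Most of this stands. The completed-participant rule is probably what was meant, and the SAP's DSMB section already has it. But the Sub-Study 3 paragraph is the one that sets the decision rule next to its boundary table, and as written it gives a different trigger from the charter, without the follow-up clause that rescues Sub-Study 1.

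A reader might infer two stronger things. One is that the mismatch materially inflates the type I error. It does not: the error moves from 0.050 to about 0.052 at most. The other is that the stated 84% power is lost. It is not, unless futility is followed; with futility ignored it is unchanged in every case simulated.

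**Conclusion.** The point holds as an internal contradiction in a stated decision rule. The enrolment trigger in Protocol 13.1 does not match the charter, the SAP's DSMB section, the general rule of its own section, or the figures printed beside it. Its cost falls on the interim decisions: under 44 weeks of uniform accrual, fewer efficacy stops at look 1, roughly two to three times as many false futility stops (3.1% to 6.0% against 1.9%), and a sample-size decision at look 2 that rests on about 64 completed outcomes instead of 100. If futility is followed, about 1 to 3 points of power go with it. Faster accrual makes the shortfall larger, and at 32 weeks or less look 1 has no completers at all.

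The direction does not depend on the accrual assumption; the size does. All stopping chances use the normal approximation, for comparison with the plan. The final test is not called into question, and the documents do not show that any look was in fact triggered by enrolment.

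**What to change.** In the Sub-Study 3 interim paragraph of Protocol 13.1, replace the enrolment trigger with the charter's: looks after 50 and 100 evaluable participants have completed the study, with a known 8-week outcome. State the same basis in the SAP's Interim Analysis section, where completion is left undefined. Add, as for Sub-Study 1, that the Hwang-Shih-DeCani boundaries are recomputed from the information actually available at each look, and give the spending parameter so that this can be done.

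The cost is a sentence or two in each document and looks about 8 weeks later than under an enrolment trigger. At 44 weeks of accrual, about 36 more participants (8 × 200/44) will have been randomised by each look. If accrual took 16 weeks or less, all 200 would be enrolled by the second look, so a stop there could no longer save recruitment.

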3. Live attenuated vaccines during the study
4. Herbal and natural remedies must be avoided

7.4 Duration of Protocol Treatment and Follow-up.

Sub-Study 1 duration of treatment is up to 2 weeks or at the time of release from quarantine. HCQ will be stopped in all patients at the time of release from quarantine

Sub-Study 3 duration of treatment is 2 months with assay to assess SARS CoV2 every 2 weeks.

7.5 Crossover from Control to HCQ arm. For Sub-Study 1 all participants are un-blinded upon symptom progression (see response assessment below) after at least 7 days of treatment or upon hospitalization if this occurs prior to 7 days of treatment. If the participant was assigned to placebo, he/she has the option to crossover to receive HCQ 400 mg po bid for up to 2 weeks or until criteria for release from quarantine are met (See 1.0 primary endpoint). During these 2 weeks of HCQ treatment, the patient will continue to complete the daily diary. An appropriately delegated study team member will call the patient daily to assess worsening symptoms and AEs. Patients who are not improving will be sent to the hospital for further care. Participants who have progressive symptoms and are subsequently hospitalized as related to COVID-19 will not be crossed over to receive HCQ at the time of unblinding.

In sub-study 3 participants who have worsening symptoms as defined as fever, significantly worsening cough, shortness of breath or hypoxia but do not require hospitalization and tests positive for SARS-CoV2 virus are allowed to cross over to receive HCQ, or treated with an alternative therapy per physician's choice. Once the positive test returns, the CRC will email IDS to initiate unblinding IDS will inform the CRC and clinical investigator if the patient was on placebo. The clinical investigator will contact the subject and inform them that if they were on placebo they would have the option of being treated with HCQ 600 mg qd. If the patient agrees, the clinical investigator will place the order in EPIC for HCQ 600 mg qd through IDS. Drug will be delivered to the patient's home. During these 2 weeks of HCQ 600 mg po qd treatment, clinical investigators will call the patient every 1-3 days depending on the severity of symptoms to assess worsening symptoms and AEs. Patients who are not improving will be sent to the hospital for further care.

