10.3 Off treatment/Off Study

Each participant has the right to withdraw from the study at any time without prejudice. The investigator may discontinue any person's participation for any reason, including adverse event or failure to comply with the protocol. Should a participant withdraw from the study, the reason(s) must be stated on the case report form, and a final evaluation of the participant should be performed. Reasons for withdrawal include the following:

Progression of Disease: Remove participant from protocol therapy at the time progressive disease is documented. Progression of disease is left to the discretion of the treating physician/ sub-Investigator; however, the following guidelines are provided to help decision making for discontinuing study drug:

Sub-study 1: Progression of disease can be confirmed if there is increase in COVID-19 symptom score for 2 days in a row and is three points higher than baseline. Once criteria for release from quarantine is met in SS1 the patient is off study. Once the person is hospitalized for COVID-19 in sub-study 1 the subject is off study. Participants who have progressive symptoms and are subsequently hospitalized as related to COVID-19 will not be crossed over to receive HCQ at the time of unblinding.

Sub-study 3: Development of new symptomology consistent with COVID-19: e.g. fever, cough, shortness of breath and SARS-COV2 test positivity would lead to unblinding. If on placebo the subject can crossover to HCQ for treatment and stay on study for 14 days or release from quarantine. If the subject was on HCQ the subject is off study and will be instructed to seek medical attention through their primary care physician

Extraordinary Medical Circumstance: If at any time the treating physician feels constraints of this protocol are detrimental to the participant's health remove the participant from protocol therapy.

Participant's refusal to continue treatment: In this event, document the reason(s) for withdrawal.

Failure to comply with protocol (as judged by the investigator such as compliance below 80%, failure to maintain appointments, etc.).

Withdrawal from treatment per patient choice: Patients may withdraw from study treatment at any point in the study for any reason. These subjects are allowed to withdraw from treatment but continue to participate with any of the other study procedures for the intended 2 month period.

Delay in treatment > 7 days due to toxicity

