11.0 ADVERSE EVENTS AND REPORTING

The timely reporting of adverse events (including toxic deaths) is required by the Food and Drug Administration. The reporting of toxicities is part of the data reporting for this study. The sponsor-investigator is responsible for ensuring that all adverse events (AEs) and serious adverse events (SAEs) that are observed or reported during the study are collected. Misuse and abuse of the study medication, medication errors and uses outside of what is foreseen in the protocol (irrespective if a clinical event has occurred) must be reported within 24 hours to the Study Sponsor/ Principal Investigator.

Adverse Events

Property of University of Pennsylvania
Confidential

The PATCH Trial

An **adverse event** (AE) is any symptom, sign, illness or experience that develops or worsens in severity during the course of the study that does not necessarily have a causal relationship with this treatment. Intercurrent illnesses or injuries should be regarded as adverse events. Abnormal results of diagnostic procedures are considered to be adverse events only if the abnormality:

- results in study withdrawal
- is associated with a serious adverse event
- is associated with clinical signs or symptoms
- leads to additional treatment or to further diagnostic tests is considered by the investigator to be of clinical significance

Adverse Event Reporting Period

The study period during which adverse events must be reported is defined as the period from the initiation of the first study treatment to the last administration of study treatment.

Post-study Adverse Event.

All unresolved adverse events should be followed by the clinical investigator until the events are resolved, the participant is lost to follow-up, or the adverse event is otherwise explained. At the last scheduled visit, the investigator should instruct each participant to report any subsequent event(s) that the participant, or the participant's personal physician, believes might reasonably be related to participation in this study.

Abnormal Laboratory Values.

A clinical laboratory abnormality should be documented as an adverse event if the abnormality is grade 1 or more and a change from baseline.

11.1 Recording of Adverse Events.

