Given the median duration of viremia is 14-20 days in mild cases, we will assume the null hypothesis that in the placebo cohort the median time to release from quarantine is 10 days from receiving a positive test. In order for HCQ to be considered more effective in this treatment setting we aim to see a median time to release from quarantine of 5 days. These values correspond to daily hazard rates of 0.069 and 0.139 respectively. We will randomize 1:1 HCQ to control and with 100 patients with 50 in the placebo arm and 50 in the HCQ arm. The one-sided z- test (alpha=.05) will have an overall 95% power to detect a significant difference between the two groups with medians of 10 and 5 days.

Based on the new CDC guidelines for quarantine release we will modify the analysis as follows: Given the median duration of viremia is 14-28 days in mild cases, we will assume the null hypothesis that in the placebo cohort the median time to release from quarantine is 14 days from receiving a positive test. In order for HCQ to be considered more effective in this treatment setting we aim to see a median time to release from quarantine of 7 days. These values correspond to daily hazard rates of 0.048 and 0.094 respectively. We will randomize 1:1 HCQ to control and with 100 patients with 50 in the placebo arm and 50 in the HCQ arm. The one-sided z- test (alpha=.05) will have an overall 93% power to detect a significant difference between the two groups with medians of 14 and 7 days.

The *hypothesis* will be tested using a one-sided test, with a z-score corresponds to the log of the hazard-ratio for recovery between the two groups. We will obtain estimates of the hazard ratio and group median survival, and 95% CI, from Cox regression. As a secondary analysis, we will stratify the analysis, and obtain separate estimates of the hazard-ratio by group. However, we are not powered to test the interaction for significance, and we do not expect significance within group.

Given that 20 subjects were recruited and treated under the old CDC guidance, we will conduct a primary analysis based on the updated 10-days from onset criterion. For the subjects who were released under the old criterion, this number will be constructed by assessing when a patient would have been released under the new rules. We will follow that with additional secondary analyses to assess the sensitivity of the results to the change in

The PATCH Trial

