In addition, at our second interim analysis for SS3, we will evaluate the conditional power based on our original assumptions. The actual effect size for this study is completely unknown. If the effect size is smaller than we anticipated but still promising, and our conditional power falls between 0.5 and 0.8, we will consider formally adjusting the sample size in SS3 to achieve a conditional power of 0.8 based on an updated understanding of the effect size (29).

Z-Value Boundaries			
	Boundaries		Information
Stage	Efficacy	Futility	Proportion
1	2.9473	-1.2318	0.2500
2	2.5825	-0.2676	0.5000
3	1.6664	1.6664	1.0000

P-Value Boundaries			
	Boundaries		Information
Stage	Efficacy	Futility	Proportion
1	0.00160	0.89099	0.2500
2	0.00491	0.60550	0.5000
3	0.04782	0.04782	1.0000

12.2 Analysis of Secondary Endpoints.

Secondary outcomes will at least be analyzed as summary statistics, with group means, odds-ratios, and 95% CIs. We may conduct exploratory analyses using regression methods appropriate for each type of measure.

Sub-Study 1: Rate of secondary infection of housemates is a binomial count by household. We will summarize the proportion or rate by group, with 95% CI. With sufficient data, we will explore subgroups, patient, and secondary patient characteristics using logistic regression. Rate of hospitalization is a binary measure. We will summarize rates by group, and estimate the odds-ratio for treatment. Adverse event rates will be summarized as a count by subject, and mean count by group, and we will estimate a rate-ratio for treatment.

Sub-Study 3: For hospital employees, Adverse event rates will be summarized as a count by subject, and mean count by group, and we will estimate a rate-ratio for treatment.

REFERENCES

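### Sub-Study 1 compares adverse-event counts per subject with no person-time denominator or common window, although routine collection stops at release from quarantine, the primary outcome

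*Protocol*

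**What the plan says.** Protocol Section 12.2 (Analysis of Secondary Endpoints) says for Sub-Study 1: "Adverse event rates will be summarized as a count by subject, and mean count by group", and then plans a rate ratio between the arms. The rate of treatment-related AEs is a stated secondary objective of the sub-study. Section 12.2 mentions no days at risk, offset or fixed window.

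Four other places determine how long each subject is observed:

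- Section 11.0, Adverse Event Reporting Period: the period runs "from the initiation of the first study treatment to the last administration of study treatment".
- Section 7.4: "Sub-Study 1 duration of treatment is up to 2 weeks or at the time of release from quarantine". It adds that "HCQ will be stopped in all patients at the time of release from quarantine".
- Section 10.3: "Once criteria for release from quarantine is met in SS1 the patient is off study".
- Table 4 in Section 9.0 places the last scheduled AE assessment on the day of release.

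Time to release is the primary outcome (Sections 2.1 and 10.2). Section 13.1 assumes for placebo that the "median time to release from quarantine is 14 days from receiving a positive test" and aims for 7 days on HCQ. The SAP supplied covers Sub-Study 3 only, so it does not add to Section 12.2 on this point.

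**The concern.** For anyone released before day 14, the efficacy event itself closes routine AE collection. The length of safety observation is therefore an outcome of treatment and not a fixed design feature. A per-subject mean count combines two things: how often AEs occur per day on drug, and how many days the subject stays on drug. If HCQ works as hoped, the second shrinks in the HCQ arm only.

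The direction matters. Whenever HCQ shortens time to release, the per-subject ratio moves in HCQ's favour, and a real daily excess of toxicity is diluted by the same factor. That is the situation in which benefit and harm would be weighed against each other.

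**Working it through.** **Inputs.** Medians of 14 v 7 days, the earlier 10 v 5 days, and stated hazards of 0.048 and 0.094 per day (Section 13.1). The alternative of 16 v 7 days (Section 13.1, interim analysis). A cap of 14 days on treatment (Section 7.4). Release no earlier than 10 days from symptom onset (Section 10.2), and testing at most 4 days after onset (Section 3.1.3).

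**The plan's own figures.** The documents give no AE ratio or AE exposure. The design effect behind the calculation can be checked through its power. With exponential release, N = 100, one-sided alpha 0.05, the printed efficacy boundaries and 45 days of accrual in a 60-day study, 14 v 7 days gives 88.0 events. Power is then 94.3% (log hazard ratio) or 91.4% (hazard difference), against 93% stated. The 45 days is not stated. It was inferred because it returns the printed maximum information of 2000.1 and fractions 0.366 and 0.674 under 10 v 5 days. Exponential release is thus consistent with the design.

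**Mean AE window.** For release time T with median m and hazard h = ln2/m, measured from first dose:

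E[min(T,14)] = (1 − exp(−14h))/h = (m/ln2)(1 − 2^(−14/m))

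With an equal, constant AE rate per day in both arms, the ratio of mean counts equals the ratio of mean windows.

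| Scenario | Placebo, days | HCQ, days | Ratio |
|---|---|---|---|
| 14 v 7 | 10.10 | 7.57 | 0.750 |
| Stated hazards 0.048, 0.094 | 10.19 | 7.79 | 0.764 |
| 16 v 7 | 10.50 | 7.57 | 0.722 |
| 10 v 5 | 8.96 | 6.18 | 0.689 |
| Placebo 14, hazard ratio 1.5 | 10.10 | 8.70 | 0.862 |
| Placebo 14, hazard ratio 1.25 | 10.10 | 9.36 | 0.927 |
| No effect on release | 10.10 | 10.10 | 1.00 |

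At 14 v 7 days a true daily ratio of 1/0.75 = 1.33 would read as 1.00.

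**Release floor.** Release needs 10 days from onset and the swab comes within 4 days of onset, so nobody can be released before about day 6 after the swab. An exponential with median 7 releases 1 − 2^(−6/7) = 45% of HCQ subjects before then. Replace T by the larger of the exponential time and 10 minus the onset-to-swab interval (assumed uniform on 0 to 4 days), and start the window at first dose. For assumed swab-to-dose lags of 0, 1, 2 and 3 days the ratios are 0.875, 0.85, 0.81 and 0.78. A floor of this kind lifts the HCQ median above 7 days. A floor that holds the medians at 14 and 7 gives smaller ratios, for example 0.63 with a 6-day floor and no lag.

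**Front-loaded AEs.** If the daily AE rate decays as exp(−kt) after first dose, expected counts are proportional to (1 − exp(−14(h+k)))/(h+k). At 14 v 7 days, assumed k of 0.1, 0.2 and 0.5 per day give:

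- k = 0.1: 4.71/5.86 = 0.804
- k = 0.2: 3.29/3.89 = 0.848
- k = 0.5: 1.67/1.82 = 0.918

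**What an offset does.** Dividing by the person-time ratio of 0.750 returns 1.00 when the rate is constant. With decay it overshoots: 0.848/0.750 = 1.13 at k = 0.2 and 0.918/0.750 = 1.22 at k = 0.5.

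**The case against.** Several counter-arguments have force.

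*Later events are not shut out.* Section 11.0 asks participants to report subsequent events they think related. Section 11.1 requires AE enquiry at every contact and covers related serious events after the study period. Section 8.4.1 keeps daily co-inhabitant calls going to 14 days after quarantine. A reader might infer that nothing after the last dose can be counted; the documents do not support that. But the stated reporting period ends at the last dose, Section 10.3 takes the patient off study at release, and Table 4 schedules no later AE assessment. What remains is largely passive, and no text says such events enter the Section 12.2 count.

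*The denominator is not spelled out.* A reader might infer that the protocol commits to dividing by subjects. It does not say so: subjects is the only denominator it names, and its optional exploratory regression neither includes nor excludes an offset. The supportable statement is that no person-time denominator is specified.

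*The 0.75 depends on the model.* This stands. Exponential release conflicts with the 10-day rule, AEs may cluster early, and AEs are recorded as episodes and not recounted daily. The ratio also returns to 1.00 if HCQ does nothing to release.

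*AEs per course is a legitimate quantity.* Shorter treatment with fewer AEs is a real consequence of the regimen. This also stands, provided the figure is labelled that way. Section 12.2 calls it a rate, and its ratio would naturally be read as relative safety.

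**Conclusion.** The point holds as a gap in a secondary safety estimate. If HCQ shortens time to release, the per-subject ratio falls below 1 with equal daily AE rates. The size is 0.75 at the design effect under exponential release and a constant AE rate. Under the other assumptions shown, it is roughly 0.78 to 0.88 with the release floor and a 0 to 3 day lag, 0.80 to 0.92 with front-loaded AEs, and 7% to 14% below 1 at hazard ratios of 1.25 to 1.5.

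Two stronger readings should be resisted. One is that 25% is a ceiling: the documents' own 16 v 7 and 10 v 5 scenarios give 28% and 31%. The other is that a biased safety result is already established: the effect is conditional on HCQ working, and Section 12.2 attaches no test or decision rule to this estimate. It is worth correcting because the error favours HCQ whenever HCQ shortens time to release, and because the correction is cheap.

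**What to change.** In Section 12.2, for Sub-Study 1:

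1. Keep the per-subject count and its ratio, labelled as AEs per treatment course.
2. Report mean days at risk by arm. Add a Poisson or negative binomial rate ratio with log(days on originally assigned study drug) as offset, counting only AEs with onset in those days. This keeps crossover HCQ days out of the placebo arm.
3. Compare arms over a common window of 14 days from first dose for every subject. Use the daily post-quarantine calls in Section 8.4.1 to ask about AEs, and reconcile Sections 10.3, 11.0 and 11.1 on whether answers after release are recorded and counted.
4. State the limits. The offset assumes a constant daily AE rate and can overstate HCQ toxicity when AEs come early (about 1.13 to 1.22 in the cases above). The fixed window includes off-drug days, so it does not equalise exposure. The three measures should be read together.

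The cost is a few sentences of analysis text, one model term and one question on calls already planned. Dosing dates should be available from the pill diary. The protocol's introduction says Sub-Study 1 was still enrolling and would be reported separately, so the change could precede its analysis. No dose, schedule or clinical rule is affected.
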